### **3.3 Subject information and informed consent**

#### **3.3.1 *Subject information***

Prior to study enrollment, the subject will be given full verbal and written information on the nature, objective, significance, expected benefits, potential risks, and expected consequences of the study. The subject will be informed that the treatment with NT 201 is not permanent and results in a temporary improvement of wrinkles for 4 – 6 months, in individual patients even longer, and that subjects will return to their baseline status afterwards. This verbal and written information will be provided by the investigator (or authorized designee) according to the provisions set forth in the Declaration of Helsinki. The obligations of the investigator are set forth in the clinical study protocol, the ICH-GCP principles (effective as of 17-JAN-1997 including ICH revision R2, 2017), and the respective national regulations governing medical research and experimentation on humans, including EU (Directive 2001/20/EG; General Data Protection Regulation) and German laws (German Medicines Act [AMG]; GCP-ordinance [GCP-V] and applicable data protection requirements). Each subject will have the opportunity to question the investigator (or authorized designee) about the study prior to giving consent.

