#### 4.3 Risk-benefit assessment

The treatment of GFL, HFL, and LCL offers predictable aesthetic results, has few adverse effects, and is associated with high patient satisfaction.

CCI

NT 201 was safe and well tolerated when all three facial areas were treated in combination, and no new safety concerns were identified during the pivotal EU UFL study. Moreover, there was no evidence of an increased incidence of treatment-emergent AEs [TEAEs], and especially those of special interest [treatment-emergent AESIs], in subjects undergoing repeat-dose treatment.

To date, all clinical studies with NT 201 in subjects with moderate-to-severe GFL, LCL or UFL (simultaneous treatment of GFL, HFL and LCL) conducted with maximum doses of up to 64 U NT 201 per treatment, have shown a good efficacy and comparable safety profile, with no evidence of new safety concerns. No new safety issues have been detected in the overall safety database. The safety results are consistent with the known safety profile of NT 201, and are supported by evidence from the comprehensive overall safety database.

In general, NT 201 is well tolerated (see current [investigator's brochure](#)). Common undesirable effects after NT 201 injection include local, generalized, or procedural AEs

---

[figure not shown]
Confidential

CCI

such as injection site hematoma, injection site erythema, and ecchymosis. Local AEs are usually mild and temporary in nature.

CCI

Additional risks that may arise in case a pandemic disease outbreak, e.g. new COVID-19 public health emergency, may affect the clinical study conduct. It is our primary goal to ensure the protection of the safety and well-being of the participating subjects.

Challenges may arise, for example, from quarantines, site closures, travel limitations, interruptions to the supply chain for the investigational product, or other considerations if site personnel or trial subjects become infected. These challenges may lead to difficulties in meeting protocol-specified procedures, and thus, might lead to protocol modifications (please refer to Section 9.2.1).

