## 6.2 Discussion of study design, including choice of control groups

The prospective, randomized, double-blind, placebo-controlled, multicenter design of the MP of this Phase 3 study was chosen to investigate the efficacy and safety of simultaneous treatment of UFL with NT 201 with minimized risk of bias by including a placebo control. Robust results are expected from the study design.

CCI

Confidential  
CCI

CCI

The observation period of 120 days (4 months) (plus 30 days if subjects have not yet relapsed to enter the OLEX period) between first injection and reinjection, represents a reasonable time that the IP will have worn off in most of the treated subjects, so that reinjection in the OLEX period can be performed safely.

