## 8.2 Treatments administered

In the MP (Cycle 1) subjects will be randomized to one of three treatment groups  
CCI

- In Group U, subjects will receive 20 U NT 201 in the GFL area, 20 U NT 201 in the HFL area, and 24 U NT 201 in the LCL area (12 U per side).
- In Group L, subjects will receive placebo in the GFL area, placebo in the HFL area, and 24 U NT 201 in the LCL area, 12 U per side.
- In Group P, all three areas will be treated with placebo.

In the OLEX period (Cycles 2 and 3), all subjects will receive NT 201 in all three areas  
CCI

Injections will be administered as described in Section 8.1.1.2.

CCI

In case of a public health emergency treatments may be halted or postponed.

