### 8.2.3 Selection and timing of doses for each subject

[figure not shown]
After a 120 day observation period following injections in cycles 1 and 2, eligible subjects will receive NT 201 reinjection **CC1** at the next cycle baseline visit (V8 for Cycle 2 and V13 for Cycle 3) according to the instructions detailed in **Section 8.1.1.2** and the injection scheme shown in **CC1**. The end-of-Cycle 1 visit V7 and the Cycle 2 baseline visit V8, as well as the end-of-Cycle 2 visit V12 and the Cycle 3 baseline visit V13 should be on the same day if eligibility criteria are fulfilled at V7 and V12, respectively.

CCI

Confidential

CCI

CCI

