### **9.2      Visit schedule**

The MP consists of a screening visit V1, which will be performed between Day -14 and Day -3 prior to randomization at baseline (V2; Day 1).

The purpose of the screening visit is to determine subject eligibility for study participation.

Baseline is defined as Day 1, which is the day of randomization and first administration of the IP.

During the double-blind MP, subjects will receive NT 201 or matching placebo once at baseline and will be followed up during five subsequent control visits (V3 to V7). V7 is also the end-of-Cycle 1 visit.

To capture long-term safety and efficacy data for this indication, eligible subjects of all three randomization groups from the MP (Cycle 1) will continue in Cycle 2, where they will receive treatment with NT 201 for all three facial areas at the Cycle 2 baseline visit V8. The end-of-Cycle 1 visit V7 and the Cycle 2 baseline reinjection visit V8 can be performed on the same day if all required eligibility criteria and none of the exclusion criteria of the OLEX period (Section 7.43) are met at V7. Reassessment for eligibility is possible within 30 days after V7 (Section 8.2.3). After treatment in Cycle 2, subjects will

[figure not shown]
be followed up during four control visits (V9 to V12) for 120 days. Control visit V12 is also the end-of-Cycle 2 visit.

After completion of Cycle 2, eligible subjects will continue in Cycle 3, where they will receive treatment with NT 201 for all three facial areas at the Cycle 3 baseline visit V13. The end-of-Cycle 2 visit V12 and the Cycle 3 baseline reinjection visit V13 can be performed on the same day if all required eligibility criteria and none of the exclusion criteria of the OLEX period (Section 7.43) are met at V12. Reassessment for eligibility is possible within 30 days after V12 (Section 8.2.3). After treatment in Cycle 3, subjects will be followed up during four control visits (V14 to V17) for 120 days. Control visit V17 is also the end-of-Cycle 3 and end-of-study visit.

[figure not shown]

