The study activities and visit schedules are shown in **CCI** for the MP and in **CCI** for the OLEX period. The clinical study protocol allows for a window of  $\pm 7$  days in scheduling of study visits for all post-baseline visits, except V3 where only a  $\pm 3$ -day window is allowed. The IP(s) must be injected by the investigator, who is trained and experienced in aesthetic BoNT treatment, at the study site. Following administration of IP(s), subjects will be observed for a minimum of 30 minutes at the site and will be asked by the investigator if any AEs have occurred since administration. Vital signs will be taken at the beginning of each study visit to ensure subject safety.

The last primary outcome visit will occur at Day  $30 \pm 7$  (V4) for each subject. For subjects not fulfilling the reinjection criteria, also not at the reassessment visit, the end-of-study visit will be performed directly and the subject will be discontinued from the study. For all other subjects, the end-of-study visit V17 will occur at Day  $120 \pm 7$  after last administration of the IP in Cycle 3. Unscheduled visits may be required in the case of AEs or premature discontinuation of the study. In this case, the final assessments as described for V17, will be performed as soon as possible. If additional safety follow-up is necessary after this visit, subjects may be contacted by telephone or be assessed in the clinic, depending on the nature of the follow-up required.

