TEAEs of the MP are defined as AEs with onset or worsening on or after date and time of the first administration of IP at V2 and before date and time of administration of IP in V8 (Cycle 2) or up to and including end of study visit (V17) in case of premature discontinuations prior to V8. For subjects who do not receive study treatment during OLEX period all AEs with onset or worsening on or after date and time of the first administration of IP up to and including end of study visit (V17) will be considered as TEAEs of MP. In case no end of study visit (V17) is performed, all AEs with onset or worsening up to and including Day 120 of MP will be regarded as TEAEs of MP.

TEAEs of the total OLEX period are defined as AEs with onset or worsening on or after date and time of the first administration of IP during OLEX period at V8 and up to and including end of study visit (V17). In case no end of study visit (V17) is performed, all AEs with onset or worsening at or after date and time of the first administration of IP during OLEX period at V8 and up to and including Day 120 of last cycle will be regarded as TEAEs of OLEX. TEAEs of Cycle 2 are defined as AEs with onset or worsening on or after date and time of the first administration of IP at V8 and before date and time of administration of IP at V13 (Cycle 3) or up to and including end of study visit (V17) in case of premature discontinuations prior to V13 or in case no study treatment is administered at V13. In case no end of study visit (V17) is performed, all AEs with onset or worsening at or after date and time of the first administration of IP at V8 and up to and including Day 120 of Cycle 2 will be regarded as TEAEs of Cycle 2. TEAEs of Cycle 3 are defined as AEs with onset or worsening on or after date and time of the first administration of IP at V13 and up to and including end of study visit (V17). In case no end of study visit (V17) is performed, all AEs with onset or worsening at or after date and time of the first

administration of IP at V13 and up to and including Day 120 of Cycle 3 will be regarded as TEAEs of Cycle 3.

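### The main-period TEAE window ends at the actual V8 injection, which can be deferred while treatment still works, so Group U is expected to be observed slightly longer than placebo

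*SAP*

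**What the plan says.** - **Window.** SAP 6.2 (Safety Endpoints) counts MP TEAEs from the V2 injection and "before date and time of administration of IP in V8 (Cycle 2) or up to and including end of study visit (V17"). The second limit covers subjects who leave before V8 or are never treated in the extension. Only if no V17 took place does the window stop at Day 120.
- **Timing of V8.** Protocol 8.2.3 says that V7 and V8 "should be on the same day if eligibility criteria are fulfilled at V7 and V12, respectively". If they are not fulfilled, Protocol 9.2 says: "Reassessment for eligibility is possible within 30 days after V7". Protocol 6.2 gives the reason for the extra time: the 120-day interval is extended, "plus 30 days if subjects have not yet relapsed to enter the OLEX period". Under Protocol 9.2, subjects still ineligible at reassessment have their end-of-study visit then, so their MP window also runs past V7.
- **Duration of effect.** Protocol 3.3.1 tells subjects that NT 201 "results in a temporary improvement of wrinkles for 4 – 6 months, in individual patients even longer". Protocol 6.2 expects the product to have worn off in most treated subjects over the 120-day interval.
- **Denominator and columns.** SAP 6.2 divides by the number of subjects treated in the cycle. The MP tables show Groups P, U and L, and a Total NT 201 column that pools U and L.
- **Endpoint.** Incidence of related TEAEs in the MP is one of two secondary safety endpoints (SAP 5.2.2).

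**The concern.** Whether a subject has relapsed by Day 120 is partly a result of treatment. Placebo subjects entered with moderate or severe lines and will mostly still have them, so they should rarely need to wait. Some Group U subjects will wait, and while they wait any new event is still counted in the MP. Group L may be affected too, through the lateral canthal lines, and it feeds the Total NT 201 column.

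The MP is the only placebo-controlled period. A crude proportion over unequal windows gives the arm with the longer window more time to collect events. At stake is how cleanly the Group U and Total NT 201 columns can be read against placebo. Efficacy and power are not involved.

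**Working it through.** The plan states no figure for window length, deferral or TEAE rates. The one related figure is the 15% assumed not to complete the MP (SAP 3). It is consistent with the plan's own count: 180 × 0.85 = 153, which is more than 150. Everything else below is an assumption, shown as a range.

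**Inputs assumed.** Incidence by Day 120 is 10%. The share *s* of Group U deferred by the full 30 days is 0.1 to 0.5, and no Group P subject is deferred. The upper end is set at one half because Protocol 6.2 expects most subjects to have worn off.

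**1. Window length.** Let dropout be *d*, leaving with an end-of-study visit at Day 60 on average. The mean window is 60*d* + (1 − *d*)(120 + 30*s*). With *d* = 0.15 in both arms:
- P: 9 + 0.85 × 120 = 111 days.
- U, *s* = 0.1: 9 + 0.85 × 123 = 113.55 days (+2.3%).
- U, *s* = 0.5: 9 + 0.85 × 135 = 123.75 days (+11.5%).

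**2. Related TEAEs, early onset.** Assume 90% of events start within 30 days of injection (9% by Day 30, 10% by Day 120). The documents support this only indirectly: Protocol 4.3 lists common effects as largely local or procedural and says "Local AEs are usually mild and temporary in nature".
- Late hazard: *h* = ln(0.91/0.90)/90 per day.
- First events added over Days 120–150: 0.90 × (1 − e^(−30*h*)) = 0.331 points per deferred subject.
- Times *s*: 0.03 to 0.17 points. The upper value is 180 × 0.00165 = 0.3 of a subject.
- With an average wait of 15 days: 0.166 × *s* = 0.02 to 0.08 points.

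**3. All-cause TEAEs, constant hazard.** 0.90 × (1 − 0.9^0.25) = 2.34 points per deferred subject. Times *s*: 0.23 to 1.17 points.

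**4. Sensitivity.**
- At *s* = 0.5 with 5% or 20% incidence: 0.08 or 0.33 points (early onset), 0.61 or 2.17 points (constant hazard).
- Equal 15% dropout multiplies the step 2 and 3 ranges by 0.85: 0.03–0.14 and 0.20–0.99 points.
- Total NT 201 against P, if no Group L subject is deferred, multiplies them by 180/270: 0.02–0.11 and 0.16–0.78 points.

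**5. Unequal dropout.** With P at 15%, the Group U dropout that cancels the gap is (120 + 30*s* − 111)/(60 + 30*s*). This is 12/63 = 19.0% at *s* = 0.1 and 24/75 = 32.0% at *s* = 0.5. Lower dropout in U than in P would widen the gap.

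**6. What a Day 120 cut-off would leave.**
- Dropout of 10% in U against 15% in P: 6 + 0.90 × 120 = 114 against 111 days, a gap of 3 days (2.7%). At 20% in U it is 12 + 0.80 × 120 = 108, or −3 days.
- If V7 is spread evenly over Days 113–127 and non-deferred subjects are reinjected at V7, the mean window is 118.25 days in P and 118.25 + 1.75*s* in U. The gap is at most 0.875/118.25 = 0.7%.

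**The case against.** **Materiality.** For the endpoint at issue, related TEAEs, the effect is a fraction of one subject. It runs against NT 201, no safety hypothesis test is visible, and no conclusion can be named that would change. This largely stands and sets the weight of the point. Late events can still enter the endpoint: related means that a causal link cannot be ruled out (Protocol 10.1.2), and under SAP 6.2 a missing causality is set to related and a worsening counts as a new event.

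**Coherence of the planned definition.** Counting from injection to injection assigns each event to one cycle, and an event in a prolonged interval is a real event after that injection. This stands, and it is why the planned table should stay. Using a Day 120 table in its place would move late events out of the comparison, in favour of NT 201.

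**Unseen text.** The reinjection criteria and parts of the safety section, including SAP 6.2.3 (cited in SAP 6.4.1), are not visible. A reader might infer that the plan has no common-window or exposure-adjusted analysis at all. The documents do not support that; only the visible text lacks one. SAP 6.2 does define time to onset by cycle, but how it will be tabulated by group cannot be seen.

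**Other causes of delay.** Protocol 8.2 adds: "In case of a public health emergency treatments may be halted or postponed". That can lengthen the window in any group and does not by itself favour one.

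**Conclusion.** The point holds as a small, mostly predictable asymmetry. With similar dropout, Group U is expected to be observed somewhat longer than Group P in the MP TEAE tables. On the stated assumptions this adds about 0.03–0.17 points for related TEAEs and 0.2–1.2 points for all-cause TEAEs. The direction is an inference from the duration of effect and the reason given for deferral. The size rests wholly on assumed incidence, onset pattern, deferral and dropout.

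Two stronger readings are tempting. A reader might infer that Group U as a whole is followed for 150 days against 120; Protocol 6.2 expects the product to have worn off in most subjects, so deferral should affect a minority. A reader might also infer that the safety comparison is materially biased or flatters NT 201. The arithmetic does not show a material effect on related TEAEs, and deferral works against NT 201. Net direction is not certain, because dropout by group is unknown.

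**What to change.** Optional, as a cheap improvement to SAP 6.2:

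1. Keep the injection-to-injection MP table exactly as planned.
2. Beside it, not in its place, show MP TEAE incidence by group limited to onset on or before study Day 120, the cut-off the SAP already uses when V17 is missing. Put later events, before V8 or up to V17, in a separate row by group so that none disappears.
3. Report MP observation days for U, L, P and Total NT 201.

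Use the study day and not the V7 visit as the cut-off, since Protocol 9.2 allows ±7 "days in scheduling of study visits for all post-baseline visits, except V3". If a redacted section already has such a table, confirming that is enough.

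The cost is one derivation from the time-to-onset variable that SAP 6.2 already defines, one descriptive table and one line of observation days. No visit, treatment or reinjection rule changes. The limitation is that the cut-off does not correct unequal dropout or a V7 held before Day 120 (step 6 of the working), which is why the observation days belong next to it.

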## 6.2 Safety Endpoints

All safety analyses will be performed on the SES. All safety tables will be presented by actual treatment group (“Group P”, “Group U”, “Group L”) at V2 in MP. In TEAE tables for total OLEX period, Cycle 2, and Cycle 3, the column headers for these three treatment groups will be “MP Group P”, “MP Group U”, “MP Group L”. TEAE tables for MP will additionally include a “Total NT 201” column for which active treatment groups (Group U and Group L) will be pooled. TEAE tables for total OLEX period, Cycle 2, and Cycle 3 will present pooled results from all three treatment groups in the fourth column, which will

be labeled "Total". For TEAE analyses over total study period, the columns "MP Group P - MP", "MP Group P - OLEX", "MP Group U", "MP Group L" and "MP Total NT 201" ("MP Group P - OLEX, MP", "Group U" and "Group L" pooled) will be presented. In column "MP Group P - MP" only AEs which occurred during MP are counted, in column "MP Group P - OLEX" only AEs which occurred in OLEX period are counted.

All analyses of laboratory values from any timepoint (Screening V1 and end-of-study visit V17) will be performed by actual treatment group at V2 in MP and in total. All analyses of vital signs from any timepoint will be performed by actual treatment group at V2 in MP, Total NT 201 (labeled "MP Total NT 201" for analysis of vital signs from visits total OLEX period) and in total.

AEs will be coded according to the MedDRA version in effect at the time the database is closed. Only TEAEs will be analyzed, which are defined as AEs with onset or worsening on or after date of the first administration of investigational product (IP) up to and including end of study visit (V17). In case no end of study visit (V17) is performed, all AEs reported during a time period corresponding to the expected cycle length will be regarded as treatment-emergent. Further details for separation of TEAEs and non-TEAEs can be found in **CCI** Non-TEAEs will be listed only.

All analyses of TEAEs will be based on the following time periods:

- Total study period
- MP (Cycle 1)
- Total OLEX period (Cycle 2 and Cycle 3)
- Cycle 2
- Cycle 3.

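### Does the SAP's rule for a missing V17 count adverse events after the V8 injection in both the main period and the extension?

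*SAP*

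**What the plan says.** SAP section 6.2 assigns each treatment-emergent event to a period. For the MP it uses three sentences in sequence.

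1. The window opens at the first injection and closes "before date and time of administration of IP in V8 (Cycle 2"), or at V17 for a subject who discontinues before V8.
2. "For subjects who do not receive study treatment during OLEX period all AEs with onset or worsening" from the first injection up to V17 count as MP events.
3. "In case no end of study visit (V17) is performed, all AEs with onset or worsening up to and including Day 120 of MP" are MP events.

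The extension window opens at the V8 injection. Cycle 2 is built in the same way. It ends at the V13 injection, or at V17 in case of "premature discontinuations prior to V13 or in case no study treatment is administered at V13". If V17 is missing, events count from "administration of IP at V8 and up to and including Day 120 of Cycle 2 will be regarded as TEAEs of Cycle 2".

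Two other statements in section 6.2 bear on the point. In the total-study tables, the MP column for Group P is one in which "only AEs which occurred during MP are counted", with a separate column for that group's extension events. The general definition says that without V17 "all AEs reported during a time period corresponding to the expected cycle length will be regarded as treatment-emergent".

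**The concern.** The third MP sentence carries no condition on treatment at V8, and its Cycle 2 counterpart carries none on V13. Elsewhere the same section does state such conditions.

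The timing needed for a clash is ordinary. Protocol section 8.2.3 wants V7 and V8 on the same day if the subject is eligible, which makes V8 nominally Day 120. Protocol section 9.2 allows 7 days either side. A subject reinjected by Day 120 who later has no V17 would then meet both the MP rule and the extension rule for events from the injection to the end of Day 120.

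For Group P, these events follow 64 U of NT 201 but would be shown under placebo. The overlap begins at an injection, and Protocol section 4.3 names local and procedural reactions as the common ones, so events on those days are plausible. Incidence of related treatment-emergent events in the MP is a secondary safety endpoint and its placebo-controlled part. Extra events in the placebo column would narrow the contrast with NT 201. Two programmers could also count the same event differently.

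**Working it through.** **Inputs.** Day 1 is baseline (Protocol 9.2). V7 is at Day 120 with a window of 7 days. V8 is on the same day or up to 30 days later (Protocol 8.2.3 and 9.2). Planned sizes are 180 in Group U and 90 each in Groups L and P (Protocol 12.1).

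**Range of V8.** Earliest 120 − 7 = Day 113. Latest 120 + 7 + 30 = Day 157.

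**Three readings of the missing-V17 sentence, for a subject injected at V8 who has no V17:**

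| V8 day | Added to the V8 rule: days in both periods | Replaces the V8 rule: days in neither period | Replaces only the V17 bound |
|---|---|---|---|
| 113 | 8 (Days 113–120) | 0 | no overlap, no gap |
| 117 | 4 (Days 117–120) | 0 | no overlap, no gap |
| 120 | rest of Day 120 | 0 | no overlap, no gap |
| 121 | 0 | Day 121 up to the injection | no overlap, no gap |
| 157 | 0 | 36 full days (121–156), then Day 157 up to the injection | no overlap, no gap |

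Only the third reading assigns every event to exactly one of the two periods.

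**Which reading the text supports.** V17 enters the MP definition in two places only: for subjects who stop before V8 (sentence 1) and for subjects not treated in the extension (sentence 2). Sentence 3 says what to do when V17 is absent, so it fills in for a bound that applies only to those subjects. For a subject injected at V8, the bound is the injection, V17 plays no part, and its absence changes nothing. In Cycle 2, V17 is likewise a bound only in the branch without a V13 injection, so the same argument holds.

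The literal reading would also let a Group P subject's MP count depend on a visit two 120-day cycles after V8, nominally 240 days later. Nothing in the plan suggests that intent, and the separate MP and extension columns for Group P speak against it.

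**Size if the literal reading were programmed.** One affected subject with no other related MP event adds 1/90 = 1.1 percentage points in Group P or L, or 1/180 = 0.6 in Group U. The documents give no rate of missing V17, so the following inputs are assumptions:

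- Group P subjects treated at V8: 76 to 90
- no V17: 2% to 10%
- V8 by Day 120: 25% to 50%
- an adverse event, related or not, in the overlap days: 5% to 15%

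Low end: 76 × 0.02 × 0.25 × 0.05 = 0.02 subjects. High end: 90 × 0.10 × 0.50 × 0.15 = 0.7 subjects, or 0.675/90 = 0.75 points.

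**Late onset without reinjection and without V17.** A late V7 can fall on Day 127, so an event could start up to 127 − 120 = 7 days after the cut-off. A reassessment visit could stretch this to 157 − 120 = 37 days. However, Protocol section 9.2 sends subjects who fail reassessment directly to the end-of-study visit, so the longer figure needs a departure from the protocol.

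**The case for a change.** The strongest counter-argument is that a programming rule should not depend on context. The condition is absent from both sentences. In Cycle 2 the preceding definition covers subjects treated and not treated at V13, so there is no directly preceding restriction to inherit, as there is in the MP. The statement about the Group P column does not settle the matter alone, because section 6.2 itself defines what counts as an MP event. The section also sets missing causality to related, so a poorly documented event would enter the endpoint.

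It stands that the words are missing and that a clause in each sentence would have been tidier. It does not stand that the omission leaves two equally good readings. The clause naming subjects untreated at V13 belongs to the rule that ends Cycle 2 at V17. Its MP counterpart is the sentence on subjects untreated in the extension, immediately before the contested one. The two definitions are drafted in parallel, so the contrast does not show that a condition was dropped in one place.

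Two side issues carry less weight. First, the general sentence speaks of events reported within the expected cycle length, while the period rules use onset or worsening to Day 120. The general wording follows Protocol section 10.1, where treatment emergence is itself defined by onset or worsening, and 120 days is the cycle length, so the two are compatible. Second, a late-onset event in a subject lost before reinjection may fall outside the MP window. Section 6.2 says "Non-TEAEs will be listed only", but the detailed rules separating the two classes are redacted, so it cannot be shown that such an event would only be listed. A fixed Day 120 cut-off is a legitimate choice. Individual window ends would trade it for unequal follow-up.

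**Conclusion.** This is a gap in wording that an analyst fills sensibly. Read with the sentences around it, the missing-V17 rule supplies an end date only where V17 would have been the end date. A reinjected subject's window closes at the next injection, and the MP and the extension do not overlap.

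If someone did program the literal reading, the overlap would be at most 8 calendar days, and only the rest of Day 120 with V8 on its nominal day. It would need a V8 injection by Day 120, no V17 about eight months later, a related event within that short span, and no other related MP event in the same subject. On the assumed rates above this is 0.02 to 0.7 Group P subjects, at most 0.75 percentage points. The event would still be counted in the extension, and no confirmatory test rests on this endpoint. Protocol sections 7.4.1 and 9.2 require the end-of-study visit after discontinuation, which keeps the number of subjects without it small.

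The conclusion rests on the visible text. The redacted rules on treatment emergence could confirm it, but it does not depend on them. No change to the plan follows.
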